10.1 Definitions and Derivations of the efficacy assessment scores

Assessment	Derivation
EASI	EASI is used to assess the severity and extent of AD; it is a composite index with scores ranging from 0 to 72, with higher values indicating more severe and/or extensive disease. Four (4) body regions are analyzed: head and neck, trunk, upper extremities and
	lower extremities. The severity of disease in each region is evaluated using 5 clinical symptoms: Erythema, Edema/Papulation, Excoriation and Lichenification. The grade of the severity of each symptom uses a 0-3 scale: 0-None, 1-Mild, 2-Moderate and 3-Severe. An average score will be calculated. However, 0.5 will be not permitted: if a sign is present, it should be at least mild (1). Additionally, for each of the 4 regions of the body, the region area score will be recorded on a scale of 0 to 6: 0-0%, 1-[1-9%], 2-[10-29%], 3-[30-49%], 4-[50-69], 5-[70-89%] and 6-[90-100%]. Area score is the total percentage of skin affected with eczema for each body region.
	The severity score is calculated for each region of the body as the sum of the severity of the 4 different signs. For example:
	Severity score (Head and neck) = severity(Erythema) + severity(Edema/Papulation) + severity(Excoriation) + severity(Lichenification)
	 Then for each region, the area score and the severity score will be multiplied. The following additional multiplies will also be used: Head and neck: severity score x area score x 0.1 Trunk: severity score x area score x 0.3 Upper extremities: severity score x area score x 0.2 Lower extremities: severity score x area score x 0.4
	The final EASI will be the sum of the total scores for each region. The range of the score is from 0 to 72. All calculations defined above are automatically conducted in the eCRF.
	The value of EASI to be used for the analysis will be the corresponding EASI score in the visit schedule: Week 2, 4 and 8. The baseline value is defined in section 8.3.1.
	Note: If any severity score of a sign and/or region area score is missing, the EASI score will be not possible to calculate, and this will be considered as missing.

Protocol title: A RANDOMIZED, VEHICLE-CONTROLLED, SAFETY AND EFFICACY STUDY OF EVO101 IN ADULT SUBJECTS WITH ATOPIC DERMATITIS

Sponsor code: EVO101-AD001

code: EPQ1001

Version number: Final 1.0

Date: 17-AUG-2023

IGA	The investigator global assessment will be on a scale of 0 to 4: 0-Clear, 1-Almost clear, 2-Mild, 3-Moderate and 4-Severe.
	Note: No additional calculation will be needed for this assessment.
	The value of the IGA score to be used for the analysis will be the corresponding IGA score in the visit schedule: Week 2, 4 and 8. The baseline value is defined in section 8.3.1.
BSA	The BSA assessment estimates the extent of disease or skin involvement with respect to AD and is expressed as a percentage of total body surface. BSA will be determined by the Investigator or designee using the subject palm = 1% rule.
	Note: No additional calculation will be needed for this assessment.
	The value of BSA percentage to be used for the analysis will be the corresponding BSA percentage in the visit schedule: Week 2, 4 and 8. The baseline value is defined in section 8.3.1 Error! Reference source not found. .
Pruritus-NRS	Pruritus will be assessed using a Pruritus Numerical Rating Scale (NRS). The Pruritus NRS is an 11-point scale used by subjects to rate their worst itch severity over the past 24 hours with 0 indicating "No itch" and 10 indicating "Worst itch imaginable." Subject assessments will be captured daily using an electronic diary.
	The value at each visit (Baseline, Week 1, Week 2, Week 3 Week 4, Week 5, Week 6, Week 7 Week 8) will be calculated as the mean of the values of the 7 previous days up to the corresponding visit. If there are less than 4 values in the prior 7 days, the value for that visit day will be set to missing.
	Values at each day (Day 1 through Day 7) will be the corresponding value collected in the day specified. The baseline value is defined in section 8.3.1.
	If more than one assessment is reported in the same day, then it will be taken that one with the worst severity following a conservative approach.

In the case of early withdrawals, a time window will be used for the efficacy assessments mentioned above, to reassign values to the correct visits using the days from baseline as follows.

Visit	Target day	Visit Window (days on treatment)
Visit 2	14	Days from Baseline ≤ 21
Visit 4	28	21 < Days from Baseline ≤ 42
Visit 8	56	42 < Days from Baseline

Statistical Analysis Plan Protocol title: A RANDOMIZED, VEHICLE-CONTROLLED, SAFETY AND EFFICACY STUDY OF EVO101 IN ADULT SUBJECTS WITH ATOPIC DERMATITIS Sponsor code: EVO101-AD001 code: EPQ1001 Version number: Final 1.0 Date: 17-AUG-2023

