10.5. Week 8 (Study Exit/Early Withdrawal)

- Perform physical exam.
- Collect AEs.
- Collect concomitant medication information.
- Measure vital signs.
- Collect ECG.
- Draw blood samples for laboratory tests and urine for urinalysis and urine pregnancy test.
- Draw blood sample for pharmacokinetic analysis.
- Collect IGA, BSA and EASI.
- Collect LSRs.
- Confirm compliance with pruritus-NRS diary.
- Confirm compliance with study drug application.
- Close e-diary and exit subject from study.

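### The SAP's early-withdrawal windows also relabel weekly itch means, so a Week 2 itch score can be mostly pre-treatment and a Week 8 score can come from about Week 6

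*SAP*

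**What the plan says.** The last rule in SAP 10.1 states that, for early withdrawals, "a time window will be used for the efficacy assessments mentioned above, to reassign values to the correct visits". The table beneath it has three rows:

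- Week 2, target day 14: "Days from Baseline ≤ 21"
- Week 4, target day 28: "21 < Days from Baseline ≤ 42"
- Week 8, target day 56: "42 < Days from Baseline"

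Four assessments stand above the rule: EASI, IGA, BSA and pruritus-NRS. Pruritus is the last of them and is not exempted.

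For pruritus, the same section says that the value at Baseline and at each of Weeks 1 to 8 "will be calculated as the mean of the values of the 7 previous days up to the corresponding visit". It adds: "If there are less than 4 values in the prior 7 days, the value for that visit day will be set to missing". SAP 8.3.6 repeats this seven-day rule. SAP 8.3.1 derives the baseline itch score from the seven diary days before baseline and numbers study days without a Day 0, Day 1 being the day of first application.

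For EASI, SAP 10.1 says: "The value of EASI to be used for the analysis will be the corresponding EASI score in the visit schedule: Week 2, 4 and 8". Protocol 10.5 uses one visit for Week 8 and for early withdrawal, and IGA, BSA and EASI are collected there. The protocol's schedule allows 1 day either side of Week 2, 2 days for Week 4 and 4 days for Week 8.

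**The concern.** A reassignment window is useful for EASI, IGA and BSA. They are read only at visits, and without it an early exit reading would carry the Week 8 label of the shared visit. Itch is different: every diary entry has its own date, so its week is known and nothing needs reassigning.

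Applied to itch, the rule joins a seven-day look-back to a Week 2 window with no lower bound. For a very early exit the look-back crosses the first application and takes in days that also make up the baseline mean. Part of the post-baseline value is then the baseline itself, and the change shrinks mechanically. At the other end, an exit soon after the 42-day cut presents itch from about Week 6 as Week 8. The SAP's version history names change in pruritus-NRS to Week 8 among the endpoints analysed by multiple imputation. The relabelled value would therefore take the place of one otherwise treated as missing.

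At stake are the itch endpoints at Weeks 2 and 8, including the 4-point improvement at Week 8. A smaller matter is which EASI, IGA or BSA value counts when an exit reading falls in a window that already holds a scheduled one.

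**Working it through.** The plan gives no dropout rate and no count for this rule, so it has no figure of its own to reproduce here. The sample-size calculation does not depend on the rule.

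**Pre-treatment days in the Week 2 itch mean.** Inputs: the seven-day look-back (SAP 10.1), no Day 0 (SAP 8.3.1), and a Week 2 window with no lower bound. For an exit on study Day d, with the exit day not counted, the look-back holds d − 1 days from Day 1 onward and 7 − (d − 1) = 8 − d pre-treatment days. If the exit day counts, there are 7 − d. If the Day 1 entry (worst itch over the past 24 hours) is treated as pre-treatment and the exit day is not counted, there are 9 − d.

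| Exit on study Day | Exit day not counted | Exit day counted | Not counted, Day 1 entry as pre-treatment |
|---|---|---|---|
| 2 | 6 of 7 | 5 of 7 | 7 of 7 |
| 3 | 5 of 7 | 4 of 7 | 6 of 7 |
| 4 | 4 of 7 | 3 of 7 | 5 of 7 |
| 5 | 3 of 7 | 2 of 7 | 4 of 7 |
| 7 | 1 of 7 | 0 of 7 | 2 of 7 |

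The mean is mostly pre-treatment for exits up to study Day 3, 4 or 5, that is, 2 to 4 days after baseline. If some diary entries are missing but at least four remain, this extends to 3 to 5 days.

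**Effect on the change score.** Take an exit on Day 4, a complete diary, the exit day not counted, and overlapping pre-treatment days that average the baseline mean B. Let P be the mean of Days 1 to 3. The Week 2 value is (4B + 3P)/7, so the change is 3(P − B)/7, or 43% of the change seen in the treated days. For an exit on Day 2 it is 1/7, or 14%.

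**Week 6 itch labelled Week 8.** Take Week 6 as Days 36 to 42 and Week 7 as Days 43 to 49, with the exit day not counted.

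- If days from baseline means study day, the first exit past the cut is Day 43. The look-back is Days 36 to 42, so 7 of 7 are Week 6 days. Exits on Days 44, 45 and 46 give 6, 5 and 4 of 7.
- If it means the simple difference from Day 1, Day 43 is 42 days from baseline and stays in Week 4. The first exit past the cut is Day 44, with Days 37 to 43 and 6 of 7 from Week 6.
- Counting the exit day lowers each figure by one.

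So at the cut, 5 to 7 of the 7 entries belong to Week 6. The protocol's Week 8 visit window is Days 52 to 60.

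**Number of subjects.** Assumption: 10-15% of 118 withdraw (12 to 18), evenly over 56 days. Exits on Days 2 to 5: 12 × 4/56 = 0.9 to 18 × 4/56 = 1.3, about 1 subject. Exits on Days 43 to 51: 12 × 9/56 = 1.9 to 18 × 9/56 = 2.9, about 2 to 3.

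**Windows already filled (EASI, IGA, BSA).** With visits on their target days and none missed, the Week 2 slot is filled for exits on Days 15 to 21, 7 of 21 days (33%). The Week 4 slot is filled for Days 29 to 42, 14 of 21 (67%). Together this is 21 of 42 (50%). Moving the visits across the protocol windows gives 6-8 of 21 (29-38%), 12-16 of 21 (57-76%) and 18-24 of 42 (43-57%).

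**The case against.** The strongest reply on itch is that the window table has rows only for Weeks 2, 4 and 8, while itch has weekly values from 1 to 8, so a programmer might never apply it to the diary. That shows the text is ambiguous, but its literal scope includes pruritus. The visible pruritus text in SAP 10.1 and 8.3.6 does not exclude pre-treatment days, although part of 8.3.6 is blacked out. The worked examples do move by a day with the counting convention, which is why ranges are shown. It is also fair that the endpoints are exploratory and that a mostly pre-treatment mean needs a very early exit. The blinded pre-analysis review in SAP 8.2 could catch single cases, but no rule for them is visible.

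On the filled windows, a reader might infer that exit readings are lost, that withdrawals then look better than they were, and that the primary endpoint is biased. The documents do not support this. SAP 8.8 places the handling of efficacy data in 8.3.5 and 8.3.6. Both are largely blacked out, as is the imputation code in 10.2, so a selection rule may exist there. If the exit value replaces the scheduled one, that bias does not arise. Nor are the slots usually filled: that holds for Week 4 only. Of the three windows, only Week 2 lacks a lower bound, and adding one for EASI, IGA and BSA is a matter of preference, since the protocol's 1-day margin is a scheduling tolerance and not an analysis window.

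**Conclusion.** The concern holds for pruritus-NRS. Read literally, the rule gives a Week 2 itch mean dominated by pre-treatment days for exits within about 2 to 5 days of baseline, and a Week 8 mean drawn from roughly Week 6 for exits just past 42 days. The first pulls change toward zero; the second misstates the time point. The effect is small: exploratory endpoints, and about 1 and 2 to 3 subjects under the assumed 10-15% evenly timed withdrawal. Early exits need not be evenly timed, so those counts are illustrative.

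For EASI, IGA and BSA the visible text lacks a tie-break, which would be needed on about half of exit days over Days 1 to 42, mainly for Week 4. That is a request for clarification, subject to the redacted sections. Neither a loss of exit data nor a direction of bias in the primary endpoint is shown.

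**What to change.** In SAP 10.1:

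1. Limit the early-withdrawal reassignment to EASI, IGA and BSA.
2. Compute each weekly itch mean only from that week's own diary days after first application, with the existing 4-of-7 rule. State whether the Day 1 entry and the visit-day entry count. Treat weeks after exit as missing under the planned missing-data method.
3. State which EASI, IGA or BSA value stands when an exit reading falls in a Week 2 or Week 4 window that already holds a scheduled one, or cross-refer to 8.3.5 and 8.3.6 if the rule is there.
4. Define the days-from-baseline count in the table cells against the days-on-treatment wording of the column header, including whether Day 1 counts as 0 or 1.

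The cost is SAP wording and a small programming change, with no new data. A few Week 2 and Week 8 itch values become missing. SAP 8.2 already provides for a new signed version before the blind is broken.

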10.2 SAS code for multiple imputation of primary endpoint

	I

Protocol title: A RANDOMIZED, VEHICLE-CONTROLLED, SAFETY AND EFFICACY STUDY OF EVO101 IN ADULT SUBJECTS WITH ATOPIC DERMATITIS

Sponsor code: EVO101-AD001

code: EPQ1001

Version number: Final 1.0

Date: 17-AUG-2023

-

Statistical Analysis Plan Protocol title: A RANDOMIZED, VEHICLE-CONTROLLED, SAFETY AND EFFICACY STUDY OF EVO101 IN ADULT SUBJECTS WITH ATOPIC DERMATITIS Sponsor code: EVO101-AD001 code: EPQ1001 Version number: Final 1.0 Date: 17-AUG-2023

10.3 SAS code for pooled proportions of secondary binary endpoints

CONFIDENTIAL

Template Ref: STL-BIS03-00-01 SAP Template v 6.0 effective 11-Mar-2021 This template is an appendix to SOP-BIS03 SAP Filing instructions: File original in TMF section 11.01.01
